2.3. The Respiratory Syncytial Virus Human Challenge Model

The RSV human challenge model was developed to not only aid understanding of RSV disease, but to also assess the efficacy of RSV antivirals, immunomodulators and vaccines. The RSV-A Memphis 37b challenge strain has been used for over 15 years by both hVIVO and others and has helped assess the efficacy of numerous RSV therapies (as reviewed by [Lambkin-Williams et al, 2018](#); [DeVincenzo et al, 2020a](#); [DeVincenzo et al, 2020b](#); [Stevens et al, 2018](#)) and vaccines ([Sadof et al, 2021](#); [Pfizer 2021](#); [Bavarian Nordic 2021](#)). Specifically, hVIVO have safely and successfully used the RSV challenge strain in over 1400 healthy participants (18 to 60 years of age) including the inoculation of 24 participants between 60 and 75 years of age. Additionally, another clone of the same strain of live RSV (Memphis 37c) has been used as an inoculation agent and was shown to be safe in over 77 healthy young adults across 3 studies. Healthy RSV challenge study participants have approximately 65% to 85% chance of becoming infected with RSV following the administration of the virus ([DeVincenzo et al, 2010](#)). Typical RSV illness is characterised by an abrupt onset of rhinitis, nasal stuffiness, malaise, myalgia (muscle aches), and sore throat. In healthy adults, the illness usually resolves without any treatment, with relief of symptoms occurring naturally within 7 to 10 days. Respiratory syncytial virus, like many viruses, can cause more substantial health issues such as myocarditis (inflammation or damage to the heart muscle). Adults and children present with RSV-related myocarditis rarely, with symptomless occurrences likely going undiagnosed in the community.

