9.4.2.2. Inferential Statistics and Significance Testing

Between-arm comparisons will be performed using appropriate hypothesis tests at the 5% 2-sided significance level, except if otherwise specified. No adjustment for multiple testing will be performed (see [Section 9.1, Statistical Hypothesis](#)).

For continuous variables (either raw data or log-transformed data) the difference in means, the standard error and the 95% 2-sided CI will be presented. In case of log-transformed variables, in addition to the previous statistics on the log-transformed data, the geometric means and geometric mean ratio and its 95% 2-sided CI for the original variable will be presented. The Wilcoxon rank-sum test, t-test, or analysis of covariance will be used, depending on whether the endpoints are normally distributed. Details on the method used for each endpoint will be provided in the SAP. Methods for checking statistical model assumptions and alternative methods of analysis if the assumptions are not fulfilled will be described in the SAP.

For categorical variables, differences in absolute frequency and/or relative risks will be presented, with their 95% 2-sided CIs. Except otherwise specified in the SAP, the Chi-square test (or Fisher Exact test) will be used to compare frequencies between study intervention arms.

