6. STUDY DESIGN

6.1. Summary of Study Design

This is a single-centre, randomised, double-blind, placebo-controlled, proof-of-concept study in healthy adult male and female participants from 18 to 55 years of age, inclusive. The primary goal of this Phase 1b study is to assess the antiviral activity of RV299 against RSV in the viral challenge model. In addition, the safety, tolerability, and PK of RV299 will be assessed.

A total of 80 participants is planned to be enrolled in this study: 40 participants on RV299 and 40 participants on placebo.

The study is divided into the following study phases:

- Screening phase: from Day -90 to Day-3 pre-human viral challenge (HVC). Historical generic screening data collected through the hVIVO generic screening process may be transferred to this study after the study-specific consent form has been signed by the participant.
- Inpatient phase: Participants will be resident in the quarantine unit for approximately 15 days (from Day -2 to Day 12). Procedures will include:
 - Pre-HVC:
 - Admission to quarantine unit on Day -2/-1.
 - Baseline assessments will be conducted as per Schedule of Events (SoE) up to Day 0, pre-challenge.
 - HVC: RSV-A Memphis 37b virus inoculation on Day 0.
 - Post-HVC:
 - Randomisation to receive RV299 or matched placebo.
 - Administration of IMP (RV299/placebo). Each participant will receive IMP twice daily (~12 hours interval) for 5 consecutive days:
 - IMP dosing to start on confirmation of RSV infection, i.e., after a positive result by qualitative integrative cycler polymerase chain reaction (qicPCR). The qicPCR of nasal wash will be performed twice daily on Days 2-5 (Day 5 morning only), or until a positive result is received, whichever is sooner. The earliest start of IMP dosing will be in the evening of Day 2 post-HVC (IMP will be initiated 12 hours \pm 1-hour post nasal wash confirmation of infection)
 - OR
 - IMP would start in the evening of Day 5, if no positive result obtained by qicPCR
 - Day 1 onwards and each day study assessments will be conducted as per SoE.
 - Participants will be discharged from the quarantine unit on Day 12 (or may remain longer at the discretion of the principal investigator [PI]/investigator).
- Outpatient phase:
 - Final visit: Day 28 (\pm 3 days).

The overall study design is depicted in

Table 1.

Table 1: Study Schematic: On-study Participant Progression

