10.1.4. Statistical Testing and Estimation

Statistical analyses for the primary and secondary endpoints will be performed using appropriate two-sided hypothesis tests at the 5% significance level.

For continuous data, an analysis of covariance (ANCOVA) will be used to compare means between the RV299 and placebo groups. The ANCOVA will have treatment group as a fixed effect and baseline viral load as a covariate, unless stated otherwise in the relevant endpoint section. Should data not satisfy the assumptions, an appropriate alternative test, e.g., Wilcoxon Rank-Sum test will be used.

P-values will be rounded to 4 decimal places. All p-values that round to 0.0000 will be presented as <0.0001 and p-values that round to 1.000 will be presented as >0.9999.

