10.1.8. Model Checking and Sensitivity Analyses

Statistical hypothesis testing will be presented using parametric tests where an ANCOVA will be the preferred statistical method. However, if the parametric test assumptions fail, non-parametric alternatives will be presented.

The normality of the error term from fitted models will be checked by performing the Shapiro-Wilk's test of normality of the residuals and producing normality probability plots of the residuals.

For cases where the normality assumption fails to hold, the treatment effect will be assessed by the non-parametric Wilcoxon rank-sum test.

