10.7.1. Primary Endpoint

10.7.1.1 Main Analysis

The primary endpoint is the AUC of RSV-A Memphis 37b viral load measured in nasal washes by qRT-PCR, from the last measurement collected prior to the first administration of IMP until the last measurement collected up to the morning of Day 12 (Quarantine discharge). The viral load data will be supplied as \log_{10} copies/mL and will be used for this main analysis and to calculate the AUC using the trapezoidal rule [1].

The AUC will be summarised for RV299 and placebo using descriptive statistics and an ANCOVA with treatment group as a main effect and the baseline value as a covariate. The baseline value will be the qRT-PCR viral load value from the last measurement collected prior to the first administration of IMP. The treatment comparison will be presented, including the LS mean treatment difference with the corresponding two-sided 95% confidence interval and p-value. The equivalent Wilcoxon rank-sum tests will be provided in place of the ANCOVA where the assumptions of the parametric test are not met.

As nasal washes are scheduled to be taken twice daily for Days 2 to 11 (and once on Day 12), in order to calculate the AUC, the actual time that the assessment was collected will be used within the AUC calculation. The AUC calculation will be based on the available non-missing assessment values between the start and end of the defined AUC time period. However, for an AUC to be derived, a participant should have at least one non-missing data recording at the start of the AUC period (e.g. date of first administration of IMP) and also at the end of the AUC time period (e.g. Day 12). In addition, the participant should have at least 1 non-missing data recording on each day between the start and end of the defined AUC time period (i.e. at least 1 out of the 2 possible assessments on each Day)). Any missing data will be reviewed at the BDRM, for its potential impact on this endpoint, and any decisions to exclude participants as a result of these criteria will be documented in the BDRM minutes. For the reporting of AUC, where appropriate, qRT-PCR values that are 'Not Detected' or 'Detected' will be re-assigned using the substitution values shown in the table in Appendix 15.1.

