Table 14.2.2.5.4	AUC of RSV Challenge Virus Viral Load by Viral Culture from Initial Administration of IMP to Quarantine Discharge (Untransformed Data) - ITT-I Population
Table 14.2.2.6	Peak Viral Load of RSV Challenge Virus by Viral Culture from Initial Administration of IMP to Quarantine Discharge - ITT-I Population

Where appropriate, these tables may be repeated on the ITT-A, ITT-B, ITT and PP Populations as .2, .3, .4 and .5 respectively.

Programming Note: It is possible that the parametric methods will fail to meet the required assumptions for the main or repeated tables. Therefore, we will provide a Wilcoxon test (see Section 10.1.4). The alternative presentation for this is shown below and will require the following footnote to be updated: [1] Comparison of RV299 and placebo using a Wilcoxon rank sum test.

Median difference in LS means [1] XX.XX
P-value [1] X.XXX

Table 14.2.2.2.1
Time to First Confirmed Undetectable Assessment of RSV Challenge Virus by qRT-PCR from Initial Administration of IMP
ITT-I Population

Time (days)	Treatment Group					
	RV299 (N=xx)			Placebo (N=xxx)		
	n	N#	Kaplan-Meier Estimate	n	N#	Kaplan-Meier Estimate
X	xx	xx	0.xxxx	xx	xx	0.xxxx
X	xx	xx	0.xxxx	xx	xx	0.xxxx
X	xx	xx	0.xxxx	xx	xx	0.xxxx
X	xx	xx	0.xxxx	xx	xx	0.xxxx
X	xx	xx	0.xxxx	xx	xx	0.xxxx
X	xx	xx	0.xxxx	xx	xx	0.xxxx
X	xx	xx	0.xxxx	xx	xx	0.xxxx
X	xx	xx	0.xxxx	xx	xx	0.xxxx
X	xx	xx	0.xxxx	xx	xx	0.xxxx
X	xx	xx	0.xxxx	xx	xx	0.xxxx
X	xx	xx	0.xxxx	xx	xx	0.xxxx
X	xx	xx	0.xxxx	xx	xx	0.xxxx
X	xx	xx	0.xxxx	xx	xx	0.xxxx
25 th percentile [1]		xx.x			xx.x	
50 th percentile [1]		xx.x			xx.x	
75 th percentile [1]		xx.x			xx.x	
p-value [2]		xxxxx				

n = number of participants with a confirmed undetectable assessment by the end of the period. N# = number of participants at risk.

[1] Percentiles are obtained from the Kaplan-Meier estimates.

[2] P-value obtained from a log-rank test compared RV299 and placebo.

Note: Time to First Confirmed Undetectable Assessment from Initial Administration of IMP = (Date of first confirmed negative test after peak qRT-PCR measurement - Date of first administration of IMP) + 1.

This table may be repeated on the ITT-A, ITT-B, ITT and PP Populations as .2, .3, .4 and .5 respectively.

This layout will be utilised for the following tables:

Table 14.2.2.3.1 Time to First Confirmed Undetectable Assessment of RSV Challenge Virus after Peak Measure by qRT-PCR from qRT-PCR following Initial Administration of IMP - ITT-I Population

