Where appropriate, these tables will be repeated on the ITT-A, ITT-B, ITT and PP Populations as .2, .3, .4 and .5 respectively.

Programming Note: It is highly likely that the parametric methods will fail to meet the required assumptions. Therefore, we will provide a Wilcoxon test (see Section 10.1.4). The alternative presentation for this is shown below and will require the following footnote update: [1] Comparison of RV299 and placebo using a Wilcoxon rank sum test.

Median difference in LS means [1]	XX.XX
P-value [1]	X.XXX

Table 14.2.3.3.1
 Total Symptom Score from 10-Item Diary Card by Assessment
 ITT-I Population

Days from IMP Administration Assessment	n	Treatment Group	
		RV299 (N=xx) Observed	Placebo (N=xx) Observed
0 Days		Change from Baseline	Change from Baseline
Assessment 1	n	XX	XX
	Mean (SD)	XX.X (XX.XX)	XX.X (XX.XX)
	GM (GSD)	XX.X (XX.XX)	XX.X (XX.XX)
	%CV	XX.XX	XX.XX
	Median	XX.X	XX.X
	Q1, Q3	XX.X, X.XX	XX.X, X.XX
	Min, Max	XX, XX	XX, XX
Assessment 2	n	XX	XX
	Mean (SD)	XX.X (XX.XX)	XX.X (XX.XX)
	GM (GSD)	XX.X (XX.XX)	XX.X (XX.XX)
	%CV	XX.XX	XX.XX
	Median	XX.X	XX.X
	Q1, Q3	XX.X, X.XX	XX.X, X.XX
	Min, Max	XX, XX	XX, XX

[Repeat for all assessments during Quarantine Period]

Note: Assessments are relative to first administration of IMP.

Note: Total symptom scores at the time of the first administration of IMP can be prior to or after dosing, depending on whether dosed in the morning or evening.

This table may be repeated on the ITT-A, ITT-B, ITT and PP Populations as .2, .3, .4 and .5 respectively.

This layout will be utilised for the following tables:

Table 14.2.3.5.1 Peak Total Symptom Score from 10-Item Diary Card by Day - ITT-I Population

The table may be repeated on the ITT-A, ITT-B, ITT and PP Populations as .2, .3, .4 and .5 as appropriate.

Table 14.2.3.6.1
 Peak Daily Symptom Score from 10-Item Diary Card
 ITT-I Population

Days from IMP Administration	Treatment Group		Placebo (N=xx)		
	RV299 (N=xx)	Observed	Change from Baseline	Observed	Change from Baseline
0 Days					
n	XX			XX	
Mean (SD)	XX.X (XX.XX)			XX.X (XX.XX)	
GM (GSD)	XX.X (XX.XX)			XX.X (XX.XX)	
%CV	XX.XX			XX.XX	
Median	XX.X			XX.X	
Q1, Q3	XX.X, X.XX			XX.X, X.XX	
Min, Max	XX, XX			XX, XX	
1 Day					
n	XX	XX		XX	XX
Mean (SD)	XX.X (XX.XX)	XX.X (XX.XX)		XX.X (XX.XX)	XX.X (XX.XX)
Median	XX.X	XX.X		XX.X	XX.X
GM (GSD)	XX.X (XX.XX)	XX.X (XX.XX)		XX.X (XX.XX)	XX.X (XX.XX)
%CV	XX.XX	XX.XX		XX.XX	XX.XX
Q1, Q3	XX.X, X.XX	XX.X, X.XX		XX.X, X.XX	XX.X, X.XX

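### If the normality check fails, the planned fallback drops the baseline adjustment and reports an undefined effect estimate with no confidence interval for the treatment difference

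*SAP*

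**What the plan says.** SAP 10.7.1.1 analyses the AUC of qRT-PCR viral load by ANCOVA, with treatment as a main effect and the last pre-dose viral load as covariate. It reports the LS-mean difference, a two-sided 95% CI and a p-value. The fallback follows: "The equivalent Wilcoxon rank-sum tests will be provided in place of the ANCOVA where the assumptions of the parametric test are not met". SAP 10.1.8 also names the Wilcoxon rank-sum test. The trigger there is the Shapiro-Wilk "test of normality of the residuals and producing normality probability plots of the residuals", with no cut-off stated.

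In SAP section 14, the main shell for Table 14.2.1.1 has rows for the LS-mean difference, its 95% CI and the p-value. The alternative shell has two rows, "Median difference in LS means" and the p-value, and its footnote mentions only a Wilcoxon rank sum test. The same two rows serve as the alternative for the symptom layout (Table 14.2.3.1.1). The programming note for the viral-load layout calls assumption failure possible. For the symptom layout it says: "It is highly likely that the parametric methods will fail to meet the required assumptions".

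For continuous variables, Protocol 9.4.2.2 says that "the difference in means, the standard error and the 95% 2-sided CI will be presented", and it leaves methods for failed assumptions to the SAP. SAP section 11 makes the mean AUC the main estimator, replacing the protocol's median.

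**The concern.** The two analyses are not equivalent. The ANCOVA estimates a baseline-adjusted mean difference, whereas the rank-sum test compares two unadjusted distributions. When the check fails, the primary result would lose its adjustment and its interval, and it would move away from the mean AUC that SAP section 11 declares as the estimator.

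The reported effect would also depend on the programmer. The label in the alternative shell could be filled with a difference of medians, a Hodges-Lehmann shift or something else, and nothing in the SAP decides between them. If this is left open, the choice may be made after unblinding with the results in view.

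**Working it through.** **1. The two paths side by side (SAP 10.7.1.1 and section 14)**

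| Item | ANCOVA path | Fallback path |
|---|---|---|
| Baseline viral load | covariate | not used |
| Effect row | difference in LS means | "Median difference in LS means" |
| Estimator defined | yes | no |
| CI for the difference | yes | no row, no method |
| p-value | ANCOVA | Wilcoxon rank-sum |

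LS means come from a fitted linear model. A rank-sum test fits none, so the fallback effect row has no definition. The only other interval text, in SAP 10.1.2, allows optional CIs for a mean or median. Those are descriptive and do not cover the treatment difference.

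**2. Reach.** The Table 14.2.1.1 layout is also used for the three sensitivity AUC tables, peak viral load by qRT-PCR, four viral-culture AUC tables and peak viral load by culture. The symptom layout covers the TSS-AUC, TSS-AUC-CFB and peak TSS tables.

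**3. An interval is available.** The Hodges-Lehmann shift is the median of all pairwise between-arm differences, and its CI inverts the rank-sum test. With 30 per arm there are 30 × 30 = 900 differences. The lower cut is k = floor(900/2 − 1.96·√(30·30·61/12)) = floor(450 − 132.6) = 317, and the upper limit is found by symmetry.

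**4. Inputs for the power check**
- Tests: "Statistical analyses for the primary and secondary endpoints will be performed using appropriate two-sided hypothesis tests at the 5% significance level" (SAP 10.1.4).
- Size: "A total of 80 participants is planned to be enrolled in this study: 40 participants on RV299 and 40 participants on placebo" (SAP 6.1).
- Infection: "approximately 65% to 85% chance of becoming infected with RSV following the administration of the virus" (Protocol 2.3). Infected per arm: 0.65 × 40 = 26 to 0.85 × 40 = 34, midpoint 30.
- Assumed, because the documents give no figure: a 0.65 SD shift, baseline–AUC correlation ρ of 0, 0.3 or 0.5, the residual shape, and a Shapiro-Wilk cut-off of 0.05.

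The visible text gives no power, SD or effect size. The relevant sections are redacted, so there is no planned figure to reproduce.

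**5. What the covariate is worth, test against test.** With normal residuals the ANCOVA residual SD is √(1 − ρ²). The shift giving 80% power is d = (1.960 + 0.842)·√(1 − ρ²)·√(2/n). For n = 26 and ρ = 0.5, d = 2.802 × 0.866 × 0.277 = 0.673. The unadjusted Wilcoxon has SD 1 and efficiency 3/π. Its power at that shift is 66%, and it is 78%, 74% and 50% at ρ = 0, 0.3 and 0.7.

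**6. What the plan loses as written.** Step 5 overstates the loss, because the plan switches only when the check fails. The simulation used 3,000 trials per scenario and 30 per arm, with AUC = ρ·baseline + √(1 − ρ²)·error + 0.65·arm. It applied the plan's switch, then the same switch to a rank ANCOVA.

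| Residuals | ρ | Plan as written | Gain from adjusted fallback |
|---|---|---|---|
| Normal | 0.5 | 80% (ANCOVA 81%) | almost nothing |
| Moderate skew (skewness 1) | 0 | 76% | about 0 |
| | 0.3 | 75% | about 3 points |
| | 0.5 | 74% | about 9 points |
| Strong skew (exponential, skewness 2) | 0 | 92% (ANCOVA 70%) | about 0 |
| | 0.3 | 86% (ANCOVA 75%) | about 4 points |
| | 0.5 | 81% (ANCOVA 80%) | about 11 points |

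With normal residuals the switch fired in about 5% of trials. Monte Carlo error is √(0.8 × 0.2/3000) ≈ 0.7 points per figure.

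**7. Type I error.** It was near 5% at 30 per arm. In separate runs of 2,500 trials at 26 and 34 per arm, the two-stage rule gave 4.1% to 6.1%, with no clear inflation.

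**The case against.** The unadjusted test is the protocol's own. Protocol 9.4.4 specifies a t-test, or a Wilcoxon rank-sum test if its assumptions fail, for the primary endpoint. Baseline adjustment there is the SAP's addition, so dropping it is a choice with an efficiency cost and not an error. That stands.

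The fallback can also do better than the ANCOVA it replaces: 92% against 70% with strong skew and ρ = 0. That stands too, and it is a reason to keep a rank-based p-value.

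A reader might infer from a test-against-test comparison (66% for Wilcoxon where ANCOVA has 80%) that the plan gives up that much power. It does not. Under normal residuals the plan would rarely run the Wilcoxon, and a material loss needs both non-normal residuals and a fairly prognostic baseline. The documents give no correlation. A reader might also take "It is highly likely that the parametric methods will fail to meet the required assumptions" as a forecast for the primary endpoint, but that note belongs to the symptom tables.

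It can further be said that SAP 10.1.4 gives the Wilcoxon only as an example, that the shell keeps an estimate row with summaries by arm, and that Protocol 9.4.2.2 speaks of means and leaves alternatives to the SAP. None of this repairs the gap. SAP 10.1.8 and 10.7.1.1 name the Wilcoxon specifically, the row has no definition, and the SAP specifies no interval for the path it was left to define.

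**Conclusion.** The point holds as a defect of specification and reporting. Followed literally, the fallback yields an undefined estimate with no interval for the treatment difference, and it departs without comment from the mean AUC. This is contingent for the viral-load tables and expected by the SAP itself for the symptom tables.

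The efficiency cost is secondary and conditional: about 0 to 9 points of power with moderate skew and 0 to 11 with strong skew, for correlations from 0 to 0.5. It rests on the assumed shift, correlations, residual shapes and Shapiro-Wilk cut-off. It would be wrong to conclude that the planned test is invalid or that its Type I error is inflated.

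**What to change.** Before unblinding:

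1. In SAP 10.7.1.1 and 10.1.8, state that the ANCOVA LS-mean difference with its 95% CI is always reported, whatever the normality check shows.
2. In both alternative shells, replace "Median difference in LS means" with the Hodges-Lehmann shift and its 95% CI, with a footnote that it is not adjusted for baseline.
3. State which p-value governs the primary conclusion when the check fails, and give the check a cut-off. Preferably use a baseline-adjusted p-value, for example from a rank ANCOVA of AUC on treatment and baseline, with the unadjusted Wilcoxon as supportive. Other adjusted methods would also serve.

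The cost is a few sentences, two shell edits and a few lines of SAS. There is one downside: a rank-ANCOVA p-value and the ANCOVA CI can disagree on significance (about 7% to 22% of simulated trials with a true effect), which is why the governing analysis must be named in advance.

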10.7.1.2 Sensitivity Analyses

1. The first sensitivity analysis of the AUC of RSV viral load measured in nasal washes by qRT-PCR will be presented for a fixed time period, from the last measurement collected prior to the first administration of IMP to the scheduled assessment occurring 6.5 days afterwards (e.g. if a participant does not have a positive qPCR then they will be dosed on Day 5 (evening) and they will be followed up to the morning of Day 12 with 14 assessments in total) – which represents the AUC over the longest possible time period over which all subjects are sampled.
2. A second sensitivity analysis of the AUC of RSV viral load measured in nasal washes by qRT-PCR will be presented for a fixed time period, which will include data from the morning assessment on Day 2 (i.e. the first qRT-PCR assessment measured) through to the morning of Day 12.
3. A third sensitivity analysis of the AUC of RSV viral load measured in nasal washes by qRT-PCR, from the last measurement collected prior to the first administration of IMP until the last measurement collected up to the morning of Day 12 (Quarantine discharge), will be presented where the AUC will be calculated using unlogged viral load data (i.e. the supplied value will be anti-logged to get a value as copies/mL).

The AUC analyses will be summarised by treatment group. The same statistical testing methods as applied to the main analysis of the primary endpoint will be applied to each sensitivity analysis. For the third sensitivity analysis, the data will be log-transformed (base 10) prior to statistical analysis.

